#### III. Objectives and Endpoints

The primary aim of this study is to determine whether distributing 100 U of onabotulinumtoxinA over less injection sites (three) is just as effective as common practice (ten).

Our secondary aim is to assess whether less injection sites has fewer complications (UTI/ hematuria) and leads to better patient satisfaction and tolerability as this procedure is done in the office while the patient is awake.

We hypothesize that a 3-site injection method is as effective as a 10-site method and will lead to higher patient satisfaction. The primary outcome will be incontinence episodes per day assessed at 3 months after BTX injection. Secondary outcomes will include voiding symptom scores and voiding diary parameters as measured by the Overactive Bladder Questionnaire-Short Form (OABq-SF), International Consultation on Incontinence Questionnaire-Short Form (ICIQ-SF), Global Response Assessment (GRA), Visual Analog Scale (VAS) on the day of injection to assess for pain, satisfaction, and tolerability, and 3-day voiding diaries to be completed throughout the study.

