#### Sample Size and Power Calculation

One hundred seventy-eight (178 patients will be randomized in this study, 89 per group to achieve 80% power to detect a non-inferiority margin difference between the group proportions of 0.15. The reference group (BTX-10) proportion is 0.85. The treatment group proportion (BTX-3) is assumed to be larger than 0.70 under the null hypothesis of inferiority. The power was computed for the case when the actual treatment group proportion is 0.85, that is both BTX-10 and BTX-3 had the same response rate of 0.85. The test statistic used is the one-sided Z test with a Type I error rate of 0.025.

Power	N1	N2	N	Reference (BTX-10) Responder Rate	BTX-3 Responder RatejH0	BTX-3 Responder Rate Ha
0.8	147	147	294	0.7	0.55	0.7
0.85	168	168	336	0.7	0.55	0.7
0.9	197	197	394	0.7	0.55	0.7
0.8	131	131	262	0.75	0.6	0.75
0.85	150	150	300	0.75	0.6	0.75
0.9	176	176	352	0.75	0.6	0.75
0.8	112	112	224	0.8	0.65	0.8
0.85	128	128	256	0.8	0.65	0.8
0.9	150	150	300	0.8	0.65	0.8

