#### Table Non Inferiority Sample size; Margin of 0.15 and expected delta=0

Power	N1	N2	N	Reference (BTX-10) Responder Rate	BTX-3 Responder Rate H0	BTX-3 Responder Rate Ha
0.8	89	89	178	0.85	0.7	0.85
0.85	102	102	204	0.85	0.7	0.85
0.9	120	120	240	0.85	0.7	0.85
0.8	63	63	126	0.9	0.75	0.9
0.85	72	72	144	0.9	0.75	0.9
0.9	85	85	170	0.9	0.75	0.9

Table Non Inferiority Sample size; Margin of 0.15 and expected delta=0

At 3 months, the percentage of patients who are successfully treated will be computed for each treatment group. Patients who exit the study early citing reasons of inadequate urge or incontinence reduction will be included in this analysis as *treatment failures*. Treatment-failure patients are otherwise known as *non-responders*.

The success rate in the BTX-3 group will be compared to that in the BTX-10 group using a non-inferiority at  $\alpha$  = 0.025 and  $\delta$  =.15 as shown earlier in this protocol.

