#### Data analyses

A biostatistician will perform all statistical analyses using SAS or similar statistical software. Descriptive statistics will be calculated. A completer analysis will be conducted for those who finish the study per protocol. The primary endpoint will be assessed comparing incontinence episodes per day at 3 months after BTX injection. This comparison will also be made for all other visits using t-tests or chi-square tests, as appropriate.

Secondary endpoints will include adverse events and comparisons between 3-site and 10-site groups looking at the GRA responses between 3-site and 10-site groups at 3 months (± 14 days) post injection, 3-day voiding diary and OABq-SF and ICIQ-SF at 3 months (± 14 days) post-injection. We will also compare post-injection VAS scores to assess for tolerability, satisfaction, and pain. Changes from baseline will also be analyzed. This comparison will also be made for all other visits using appropriate statistical tests.

In addition to a completer analysis, we also plan on conducting an intent to treat analyses which will identify any subject not assessed at 3 months after the first BTX injection as a treatment failure. In order to assess for all possible situations, 4 different scenarios will be run: 1) All dropouts will be considered non-responders for both groups 2) All dropouts will be considered responders for both groups, 3) Dropouts in the BTX 10 group will be considered responders and those in the BTX 3 group, non-responders, and 4) Dropouts in the BTX 10 group will be considered non-responders while those in the BTX 3 group, responders.

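### The dropout rules cover the success rate but not mean episodes per day, so patients who exit for lack of effect vanish from a comparison the plan also calls primary

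*Combined protocol and SAP*

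**What the plan says.** Two outcomes carry primary status. Section III states: "The primary outcome will be incontinence episodes per day assessed at 3 months after BTX injection". Section VII, Primary Effectiveness, instead defines a responder (at least a halving of urgency incontinence episodes at 3 months) and sets the non-inferiority hypothesis, with its 0.15 margin, on the success proportions. Data analyses then returns to the count: "The primary endpoint will be assessed comparing incontinence episodes per day at 3 months after BTX injection". It continues: "This comparison will also be made for all other visits using t-tests or chi-square tests, as appropriate".

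Dropouts are handled in three places:

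- After the sample-size tables: "Patients who exit the study early citing reasons of inadequate urge or incontinence reduction will be included in this analysis as" treatment failures.
- In Section IV (end of Injection Procedure) and again in Data analyses: the intent-to-treat analysis counts anyone not assessed at 3 months as a failure.
- In Data analyses: four scenarios set dropouts to responder or non-responder, by arm.

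The only other analysis set named is a completer analysis. No imputation, model or other missing-data method is given for episodes per day.

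**The concern.** All three rules recode a yes/no outcome, and none can be applied to a mean. A t-test needs an observed value, so at each visit it runs on the patients who returned a diary. The plan itself foresees patients leaving because the injection did not work. It keeps them as failures in one analysis and, by omission, loses them from the other.

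This loss depends on outcome. If the 3-site arm truly has more failures, and failures leave at similar rates in both arms, that arm loses more of its high counts and the mean difference moves toward zero. The aim is to show that 3 sites work as well as 10, so this is the favourable direction. Because Section III and Data analyses label episodes per day primary, a reader could take a small mean difference as confirmation. The failure rule is also tied to month 3, so the comparisons at 6, 9 and 12 months have no counterpart to it.

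**Working it through.** **1. The plan's own figure.** Inputs: "The test statistic used is the one-sided Z test with a Type I error rate of 0.025"; "The reference group (BTX-10) proportion is 0.85"; under the alternative "both BTX-10 and BTX-3 had the same response rate of 0.85"; and "89 per group to achieve 80% power to detect a non-inferiority margin difference between the group proportions of 0.15".

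n per arm = (1.960 + 0.842)² × 2 × 0.85 × 0.15 / 0.15² = 7.849 × 0.255 / 0.0225 = 88.95, so 89. Power at 89 is 80.0%. The stated figure reproduces. The 178 is the bare formula total, so the sample size implies no dropout rate that could be used here.

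**2. Model for the mean.** From the plan: success 0.85 (10-site) and 0.70 (3-site, the value at the margin). Assumed, because the documents give none of these: baseline mean 4 episodes/day; month-3/baseline ratio log-normal with SD σ = 0.8 or 1.2 on the log scale, independent of baseline; a share w of failures leaves before month 3.

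With z_p the normal quantile of p:

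- μ = ln 0.5 − σ z_p, which makes P(ratio ≤ 0.5) = p
- full mean M = 4 exp(μ + σ²/2)
- mean among those who stay = M × [1 − w Φ(σ − z_p)] / [1 − w(1 − p)]

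**3. Worked case, σ = 0.8, w = 0.30 in both arms.**

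- 10-site: M = 1.202; among stayers 1.202 × (1 − 0.3 × 0.4065) / (1 − 0.045) = 1.105
- 3-site: M = 1.811; among stayers 1.811 × (1 − 0.3 × 0.6086) / (1 − 0.09) = 1.626
- true difference 0.609; observed 0.521, or 85.7% of it

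Total loss here is 4.5% and 9% of the arms, about 4 and 8 patients of 89.

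**4. Range.** Observed difference, and its share of the true difference:

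| Failures leaving, 10-site v 3-site | σ = 0.8 (true 0.609) | σ = 1.2 (true 1.005) |
|---|---|---|
| 10% v 10% | 0.582 (95.7%) | 0.954 (94.9%) |
| 20% v 20% | 0.553 (90.9%) | 0.897 (89.2%) |
| 30% v 30% | 0.521 (85.7%) | 0.835 (83.0%) |
| 40% v 40% | 0.486 (79.8%) | 0.766 (76.2%) |
| 20% v 30% | 0.488 (80.2%) | 0.782 (77.7%) |
| 30% v 20% | 0.587 (96.4%) | 0.950 (94.5%) |
| 30% v 15% | 0.618 (101.5%) | 1.005 (100.0%) |
| 30% v 10% | 0.648 (106.5%) | 1.058 (105.2%) |

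With equal rates the shrinkage is about 9-11%, 14-17% and 20-24% at w = 20%, 30% and 40%. It is gone at 30% v 15% and reversed at 30% v 10%.

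**5. Size against noise.** Further assuming a gamma baseline of shape 1 to 4, the standard error of the mean difference at 89 per arm is about 0.25-0.37 (σ = 0.8) or 0.50-0.69 (σ = 1.2). The bias is then roughly 0.15-0.21 standard errors at w = 20% and 0.24-0.34 at w = 30%.

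**6. Cross-check with a cruder model.** Take 1 episode/day in responders and 4 in failures. The true difference is 0.45. If 25% of failures leave each arm, the stayers' means are (0.85 + 0.45)/0.9625 = 1.351 and (0.70 + 0.90)/0.925 = 1.730. The difference is 0.379, or 84%. With 50% v 25% leaving (10-site v 3-site) it is 108%. Same pattern.

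**The case against.** **The confirmatory test is protected.** The only hypothesis, margin, alpha and sample size concern the success proportion. There, lack-of-effect exits are failures and four extreme scenarios are run. The mean comparison has no margin, so it cannot formally establish non-inferiority. This stands. A reader might infer that the trial's main conclusion is biased; the documents do not support that.

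**The direction is not fixed.** A reader might infer that the mean is always pulled toward similarity. That needs failures to leave at similar rates, or more often in the 3-site arm. Patient blinding makes similar rates plausible but does not guarantee them.

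**Loss may be small.** Section IV keeps 3-month non-responders in follow-up and collects their data. It also lets patients who cannot attend visits 4 to 7 return diaries and questionnaires by mail. Only the 2-week follow-up visit precedes month 3. These provisions should limit w, and nothing in the documents supports 30-40%. They do not supply a value for a patient who exits. Whether the bias grows after month 3 cannot be determined: repeat injections and discretionary management also enter the later means.

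**The text is silent rather than wrong.** The plan does not say that dropouts are excluded from the t-tests; that follows from the absence of any rule. Nor is the week-2 diary thrown away. It has its own comparison and is simply not used to inform month 3. For the questionnaire scores the plan says only that suitable tests will be chosen, so the point is firm for episodes per day alone.

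**Conclusion.** The concern holds for the episodes-per-day comparison. The plan treats the same patients as failures in one analysis and leaves them out of another that it also calls primary. Under equal exit rates and the assumed inputs, a true 3-site deficit in the mean is understated by about 9-11% if 20% of failures leave and 14-17% if 30% leave; below about 20% the shrinkage is under 10%. It vanishes or reverses if 10-site failures leave about twice as often or more. At 89 per arm it is a fraction of a standard error. Exit rate, baseline mean and spread are all assumed, so the figures illustrate and do not predict. The non-inferiority test of proportions stands as written. The change is worth making because it is cheap and because the plan's own wording gives the mean comparison weight it has not been equipped to carry.

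**What to change.** In Section VII, Data analyses:

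1. Replace the visit-by-visit t-tests for episodes per day with one repeated-measures mixed model. Include all randomised patients with any post-injection value, with terms for arm, visit, arm-by-visit and baseline value. Report the month-3 arm difference with its 95% CI. The same model may serve the other diary and questionnaire scores.
2. Add a sensitivity analysis in which a patient who exits citing inadequate urge or incontinence reduction is given the baseline value at later visits. This carries the existing failure rule into the mean.
3. State that episodes per day supports the responder non-inferiority test, and align Section III with this. That test and its dropout rules are unchanged.

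The cost is wording and some programming, with no new patients, visits or data. It should be settled before outcome data are seen by arm.

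The gain is partial. The model assumes missing at random given baseline and earlier diaries, and the baseline value is a convention. In simulation under the same assumptions at w = 30%, a model using a week-2 diary correlated 0.5-0.7 with month 3 left 8-14% shrinkage, against 14-17% for observed cases. Baseline assignment left 1% (σ = 0.8) to 11% (σ = 1.2). Both err on the same side in these cases, so the two results should not be presented as bracketing the truth. Neither addresses the effect of repeat injections on the later means.

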#### VII. Data Analysis

**Statistical Analysis** 

#### Primary Effectiveness

The primary efficacy endpoint is defined as at least a 50% reduction in number of urgency related incontinence episodes at 3 months. The number of urgency incontinent episodes per day is measured as the average of two, 3-day, consecutive bladder diaries. Patients shall be classified as treatment successes or treatment failures based on this criterion.

The primary hypothesis is that the proportion of patients who are treatment successes with BTX-3 is non-inferior with a margin of 15% to that with BTX-10 at 3 months.

 $H_{o}: p_{BTX-3} \le p_{BTX-10} - 0.15 \text{ vs}$   $H_{a}: p_{BTX-3} > p_{BTX-10} - 0.15$ 

In the hypothesis equations, 0.15 is the clinical equivalence margin for the non-inferiority test of this hypothesis.

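### Scoring every patient not assessed at 3 months as a failure in both arms can lift the non-inferiority error above 0.025 when loss is similar across arms and largely unrelated to outcome, and no analysis is named as decisive

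*Combined protocol and SAP*

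**What the plan says.** Under Primary Effectiveness, success is at least a 50% reduction in urgency incontinence episodes at 3 months, and the hypothesis is that success with 3 sites is "non-inferior with a margin of 15% to that with BTX-10 at 3 months". Under Sample Size and Power Calculation: "The test statistic used is the one-sided Z test with a Type I error rate of 0.025".

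Three statements deal with patients who lack a 3-month result.

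- Below the second sample-size table: "Patients who exit the study early citing reasons of inadequate urge or incontinence reduction will be included in this analysis as" failures. This covers only exits for lack of effect.
- Under Data analyses, and also in Methodology, the intent-to-treat analysis is wider. It will "identify any subject not assessed at 3 months after the first BTX injection as a treatment failure", whatever the reason.
- Data analyses then lists four dropout scenarios. The first two are "1) All dropouts will be considered non-responders for both groups 2) All dropouts will be considered responders for both groups". The third counts 10-site dropouts as responders and 3-site dropouts as non-responders; the fourth does the reverse.

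Data analyses also plans a completer analysis, limited to patients who see the study through under the protocol. No expected loss rate is given, and nothing says which of these analyses decides non-inferiority.

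**The concern.** In a superiority trial, giving all missing patients in both arms the same bad outcome usually works against the claim. In a non-inferiority trial it can work for it. If the two arms lose similar shares for reasons unrelated to outcome, the same recoding removes more successes from the arm that has more of them, so the observed rates move together. A 3-site method that is truly 15 points worse is then tested as if the gap were smaller.

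The rule also adds failures to both arms and so raises the variance. That makes it harder for a truly equivalent 3-site method to succeed. The sponsor therefore risks a higher chance of a false claim and a lower chance of a true one from the same rule.

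**Working it through.** **Inputs.** All are from Data Analysis: "89 per group to achieve 80% power to detect a non-inferiority margin difference between the group proportions of 0.15"; a 10-site success rate of 0.85; a 3-site rate "assumed to be larger than 0.70 under the null hypothesis of inferiority", that is, a boundary of 0.70; one-sided 0.025. The loss rate m is not in the documents; 5% to 20% is an assumption. Patients not assessed at 3 months and dropouts are treated as one group.

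**1. Reproduce the plan's figure.** With unpooled variance,
n = (1.960 + 0.842)² × (0.85×0.15 + 0.85×0.15) / 0.15² = 7.849 × 0.255 / 0.0225 = 88.95, so 89 per arm, with power 80.02%. This matches the plan and includes no allowance for loss.

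**2. Effect of the rule.** With equal loss m unrelated to outcome, each success rate p becomes p(1-m), so d becomes (1-m)d. Example at m = 10%:
- rates 0.85×0.9 = 0.765 and 0.70×0.9 = 0.630; difference 0.135
- standard error = √[(0.765×0.235 + 0.630×0.370)/89] = 0.0681
- error ≈ Φ[(0.15 - 0.135)/0.0681 - 1.960] = Φ(-1.740) = 0.041

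Full binomial enumeration of the same Z test gives 0.042.

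**3. All planned treatments of loss, by exact enumeration.** Error is at true 0.85 v 0.70; power is at true 0.85 in both arms. Scenarios use 89 per arm; completers use 89, 85, 80, 76 and 71.

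| Loss in each arm | 0% | 5% | 10% | 15% | 20% |
|---|---|---|---|---|---|
| Missing = failure (scenario 1): error | 0.026 | 0.033 | 0.042 | 0.050 | 0.060 |
| Missing = failure: power | 0.80 | 0.72 | 0.66 | 0.61 | 0.58 |
| Scenario 2: error | 0.026 | 0.034 | 0.046 | 0.061 | 0.080 |
| Scenario 3: error | 0.026 | 0.004 | 0.0005 | <0.0001 | <0.0001 |
| Scenario 3: power | 0.80 | 0.44 | 0.14 | 0.03 | 0.003 |
| Completers: error | 0.026 | 0.026 | 0.027 | 0.028 | 0.027 |
| Completers: power | 0.80 | 0.78 | 0.77 | 0.75 | 0.71 |

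**4. Dependence on the pattern of loss (missing = failure, exact).**
- Unassessed patients all true failures, or sharing one true success rate across arms: the difference stays 0.15 and the error stays near nominal (0.0255 to 0.0259 at 5 to 10% loss).
- Unassessed patients succeed at half their arm's rate (0.425 and 0.35): at 10% loss the difference is 0.15 - 0.10×(0.425 - 0.35) = 0.1425 and the error 0.033; at 20% loss it is 0.042.
- 15% lost in the 3-site arm v 10% in the 10-site arm: rates 0.595 and 0.765, difference 0.17, error 0.012.
- 5% v 10%: rates 0.665 and 0.765, difference 0.10, error 0.114.
- The two losses offset when the 3-site loss is 0.85/0.70 = 1.21 times the 10-site loss.

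**5. Completers defined at month 12.** For illustration, let 30% of month-3 failures and 10% of month-3 responders leave before month 12. The completer rates become 0.85×0.9/(0.85×0.9 + 0.15×0.7) = 0.879 and 0.70×0.9/(0.70×0.9 + 0.30×0.7) = 0.75. The gap is then 0.129 and the exact error 0.056.

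**6. The alternative.** Multiple imputation within arm, simulated under equal random loss (20,000 trials, 20 imputations, Rubin's rules), gives error 0.027 to 0.028 and power 0.78, 0.76, 0.73 and 0.71 at 5, 10, 15 and 20% loss.

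**The case against.** - **The inflation is not automatic.** This stands. It rests on a loss rate that the documents do not give and on a pattern of loss that nobody knows yet. Step 4 shows it vanishing or reversing. A reader might infer that the test simply fails to hold 0.025, or that the error rises with each missing diary; neither holds in general. Methodology also keeps patients who miss visits in the study and accepts diaries by mail, which should limit loss at month 3.
- **The plan already has a sound analysis.** This stands in part. Under random loss the completer analysis performs as well as multiple imputation, so in that setting the remedy shows no numerical gain over the plan. A reader who inferred that the plan contains no usable analysis would be wrong. But the completer analysis is not named as decisive, and finishing the study may mean 12 months, which can select on events after the endpoint (step 5).
- **Scenario 3 guards against a false claim.** It does. It is not hopeless at low loss, with power 0.44 at 5%, but at 10% or more a truly equal arm would rarely pass, and nothing says what follows if it fails.
- **The 0.025 belongs to the primary comparison, not to this rule.** The documents leave this open, which is part of the problem: the plan does not say which analysis carries the claim.
- **Non-assessment could be part of a composite endpoint, for which 0.025 would hold.** This fails. Primary Effectiveness defines success by the 50% reduction alone.

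**Conclusion.** The concern holds in conditional form. If loss is similar across arms and largely unrelated to outcome, the intent-to-treat rule raises the one-sided error from 0.026 with no loss to between 0.033 and 0.060 at 5 to 20% loss, and cuts power at true equality from 0.80 to between 0.72 and 0.58. Scenario 2 inflates the error somewhat more; scenario 3 controls it, but with little power once loss reaches 10%. These figures assume 89 per arm, the unpooled Z test, true rates of 0.85 and 0.70 (0.85 in both arms for power), and an assumed loss range.

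The documents do not support the stronger conclusion that the trial's error rate is broken whatever happens. With little loss, with mostly true failures among the unassessed, or with heavier loss in the 3-site arm, the error is nominal or lower. What the plan lacks is control over which case applies, and a named deciding analysis that does not depend on it so strongly. The change should be made before the data are analysed.

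**What to change.** In the intent-to-treat non-inferiority test:

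1. Keep failure for patients who leave because of inadequate reduction, as the text below the sample-size table already says.
2. For all other patients unassessed at month 3, impute success by multiple imputation within arm, using the baseline and 2-week diaries and prior-BTX status.
3. Name this as the analysis that decides non-inferiority, and state the expected share unassessed at month 3.
4. Base the supporting completer analysis on patients assessed at month 3, not on those who finish the study.
5. Report scenarios 1 to 4 as the corners of a tipping-point grid over the assumed success rates of unassessed patients in each arm. No fixed pass threshold on the grid is needed; the documents give no basis for one.

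The cost is revised analysis wording and a little more programming, with no new data or patients. The downside is that imputation assumes data missing at random given what is collected; the grid then tests that assumption.

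### Dropout scenarios 2, 3 and 4 recode as responders patients whom the plan already counts as treatment failures, which can change the robustness conclusion

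*Combined protocol and SAP*

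**What the plan says.** Three statements in the combined protocol and SAP bear on patients who leave before the 3-month assessment.

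- Section VII, text after the sample-size tables, on the 3-month success-rate comparison: "Patients who exit the study early citing reasons of inadequate urge or incontinence reduction will be included in this analysis as" treatment failures, a term the plan equates with non-responders. It does not mention patients who leave for other reasons, and it sets no time limit on an early exit.
- Section VII, Data analyses, and in the same terms Section IV, Methodology: the intent-to-treat analysis will "identify any subject not assessed at 3 months after the first BTX injection as a treatment failure", whatever the reason.
- Section VII, Data analyses: four scenarios follow. Scenario 1 makes dropouts non-responders in both arms. The next reads "2) All dropouts will be considered responders for both groups". Scenario 3 makes them responders in BTX-10 only, and scenario 4 in BTX-3 only. Dropout is not defined, and no scenario sets lack-of-effect exits apart.

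**The concern.** Best-case and worst-case scenarios exist to show how far the conclusion depends on outcomes nobody observed. A patient who leaves saying the treatment did not reduce urgency or incontinence is not in that position, because the plan has already classed that patient as a non-responder. Scenarios 2, 3 and 4, followed literally, reverse that classification in at least one arm.

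The error has a direction. If 3 sites work less well than 10, more BTX-3 patients would be expected to leave for lack of effect. Scenarios 2 and 4 would credit them to BTX-3 as successes. Scenario 3 errs the other way, by crediting BTX-10. What is at stake is whether the scenario results can be trusted as a check on the non-inferiority conclusion.

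**Working it through.** **1. The plan's own figure.** Inputs from Section VII: "The test statistic used is the one-sided Z test with a Type I error rate of 0.025"; "89 per group to achieve 80% power"; "The reference group (BTX-10) proportion is 0.85"; power computed for the case where "both BTX-10 and BTX-3 had the same response rate of 0.85"; and "0.15 is the clinical equivalence margin for the non-inferiority test of this hypothesis". With unpooled variance, n = (1.960 + 0.842)² × (2 × 0.85 × 0.15) / 0.15² = 7.849 × 0.255 / 0.0225 = 88.95, so 89 per arm. The stated figure is reproduced, and the same formula is used below.

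**2. How a patient who exits before month 3 for lack of effect is coded.**

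| Analysis | If in BTX-3 | If in BTX-10 |
|---|---|---|
| 3-month comparison (after the sample-size tables) | failure | failure |
| Intent to treat | failure | failure |
| Scenario 1 | failure | failure |
| Scenario 2 | responder | responder |
| Scenario 3 | failure | responder |
| Scenario 4 | responder | failure |

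**3. Illustration.** The documents give no dropout rate, so these counts are assumptions: 89 per arm, 8 unassessed per arm, lack-of-effect exits 4 (BTX-3) and 1 (BTX-10), and successes among the 81 assessed 67 and 69.

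Lower limit = d − 1.96 × √[p3(1−p3)/89 + p10(1−p10)/89], where d = p3 − p10, compared with −15 points.

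- Scenario 2 as written: 67+8 = 75 and 69+8 = 77 successes. d = 0.8427 − 0.8652 = −0.0225; SE = √(0.001489 + 0.001311) = 0.0529; limit = −0.0225 − 0.1037 = −0.126.
- Scenario 2 with lack-of-effect exits kept as failures: 75−4 = 71 and 77−1 = 76. d = 0.7978 − 0.8539 = −0.0562; SE = √(0.001813 + 0.001401) = 0.0567; limit = −0.0562 − 0.1111 = −0.167.

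| Analysis | BTX-3 | BTX-10 | Difference (points) | Lower limit | Non-inferior? |
|---|---|---|---|---|---|
| Intent to treat, same as scenario 1 | 67/89 | 69/89 | −2.2 | −14.7 | yes |
| Scenario 2, as written | 75/89 | 77/89 | −2.2 | −12.6 | yes |
| Scenario 2, exits kept as failures | 71/89 | 76/89 | −5.6 | −16.7 | not shown |
| Scenario 3, as written | 67/89 | 77/89 | −11.2 | −22.7 | not shown |
| Scenario 3, exits kept as failures | 67/89 | 76/89 | −10.1 | −21.7 | not shown |
| Scenario 4, as written | 75/89 | 69/89 | +6.7 | −4.8 | yes |
| Scenario 4, exits kept as failures | 71/89 | 69/89 | +2.2 | −9.8 | yes |

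**4. Dependence on the assumed split.** With the other counts unchanged, scenario 2 with exits kept as failures gives 73/89 v 75/89 and a limit of −13.2 if the exits are 2 v 2, and 72/89 v 75/89 and a limit of −14.5 if they are 3 v 2. Both remain non-inferior.

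**5. Behaviour at the null.** Take true success rates of 0.85 (BTX-10) and 0.70 (BTX-3). Suppose a fraction q of the failures in each arm leave for lack of effect and nobody else leaves. Scenario 2 then sees rates of 0.70 + 0.30q and 0.85 + 0.15q; scenario 4 sees 0.70 + 0.30q and 0.85. The chance of declaring non-inferiority is Φ[(0.15 − (p10 − p3))/SE − 1.96].

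- q = 0.10, scenario 2 (0.73 v 0.865): Φ(0.015/0.0594 − 1.96) = 4.4%.
- q = 0.20, scenario 2 (0.76 v 0.88): Φ(0.030/0.0569 − 1.96) = 7.6%.
- q = 0.10, scenario 4 (0.73 v 0.85): Φ(0.030/0.0604 − 1.96) = 7.2%.
- q = 0.20, scenario 4 (0.76 v 0.85): Φ(0.060/0.0590 − 1.96) = 17.3%.
- Exits kept as failures (0.70 v 0.85): Φ(−1.96) = 2.5% for any q.

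Scenario 3 goes the other way: 1.4% at q = 0.10 and 0.7% at q = 0.20.

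**The case against.** The strongest reply is that the scenarios are bounds. The plan introduces them as covering every possible situation, and a bound may include implausible codings. Scenario 1 equals the intent-to-treat rule, and no section says that scenario 2 or 4 decides the trial. In the illustration, scenario 3 as planned already fails by a wide margin (−22.7), so the planned set does not hide the fragility. The completer analysis on the same counts (67/81 v 69/81) gives −13.8, and intent to treat gives −14.7; both are non-inferior. The plan also lets the month-3 diary be returned by mail and keeps non-responders in follow-up, which should limit the number unassessed.

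Most of this stands, and it limits the point. It does not answer the core of it: a bound on unknown outcomes should not vary outcomes the plan has settled, and the text neither labels the scenarios as sensitivity analyses nor defines dropout.

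Two stronger readings are tempting. A reader might infer that the text after the sample-size tables conflicts with the intent-to-treat rule on patients who leave for other reasons. It does not. It is silent on them, the intent-to-treat rule covers them, and for lack-of-effect exits before month 3 the two agree. Nothing says that other leavers are to be left out of the denominator. A reader might also infer that the trial's type I error is inflated to the rates in step 5. Those rates would apply only if scenario 2 or 4 were used to declare non-inferiority, which the plan does not say.

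**Conclusion.** The point holds as an inconsistency in the scenario definitions. Patients whom the plan counts as failures become responders in both arms under scenario 2, in BTX-10 under scenario 3 and in BTX-3 under scenario 4. The scenario results, and with them the robustness conclusion, can change but need not. The scenario 2 reversal in step 3 rests on an assumed 4 v 1 split and disappears at 2 v 2 or 3 v 2. At the null, scenarios 2 and 4 are too lenient when lack-of-effect exits are recoded, and scenario 3 is too strict. The size rests on assumed dropout counts, on the assumed 10% to 20% of failures leaving, and on the unpooled normal approximation that reproduces the plan's sample size. The documents do not support the claim that the non-inferiority result must turn on this. It should be corrected before outcomes are compared by arm.

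**What to change.** In Section VII, Data analyses:

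- Replace dropouts in the four scenarios with *patients with unknown month-3 status*.
- State that a patient who exits before the month-3 assessment citing inadequate urge or incontinence reduction is a failure in the intent-to-treat analysis and in all four scenarios.
- Label the four scenarios as sensitivity analyses.

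In the text after the sample-size tables, state that the rule of Sections IV and VII (not assessed at 3 months means failure) covers all other leavers in the intent-to-treat analysis. Record the exit reason on a fixed list when the patient exits, before outcomes are compared by arm.

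The cost is a few lines of text and one case report form field; treatment, visits and sample size do not change. There are two downsides to disclose. Scenarios 2 and 4 become less favourable to BTX-3. Scenario 3 becomes a slightly less severe stress test: −22.7 moves to −21.7 in the illustration. With few dropouts that can reverse its result. For example, with 4 dropouts per arm, 2 of them for lack of effect in each arm, and 72/85 assessed successes per arm, scenario 3 moves from −15.5 (72/89 v 76/89, not shown) to −13.5 (72/89 v 74/89, non-inferior).
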